9.2 Safety and other evaluations

not applicable

9.3 Adverse Events and Serious Adverse Events

not applicable

10. Statistical Analysis

10.1 General Methods

For descriptive statistical analysis, measurement data conforming to a normal distribution are expressed as mean \pm standard deviation; measurement data not conforming to a normal distribution are expressed as median (interquartile range); count data are expressed as rates or proportions. For comparing two groups of measurement data with normal distribution and equal variance, an independent two-sample t-test is used; for comparing two groups of measurement data not conforming to normal distribution and equal variance, a non-parametric Mann-Whitney U test is used. For count data in contingency tables, Pearson's chi-square test is used if conditions are met; otherwise, Pearson's chi-square test with continuity correction or Fisher's exact test is applied. All tests are two-tailed, with $P < 0.05$ considered statistically significant.

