5.1 Overall Design

A total of 182 patients with first-ever anterior circulation AIS (Acute Ischemic Stroke) hospitalized in the Neurology Department at the Northern Campus of our hospital will be selected as the observation group, and 91 healthy individuals undergoing physical examination will be selected as the control group. For AIS patients, 10 ml of elbow venous blood will be collected at admission and then at 24 hours and 7 days after stroke onset. For healthy individuals, 10 ml of fasting elbow venous blood will

be collected once. The dynamic changes and differential expression characteristics of a group of neuroinflammatory molecules, including KLK10, sTREM2, and GFAP in plasma will be observed. The early changes (at admission and 24 hours after onset) of these neuroinflammatory molecules in plasma will be compared and analyzed in relation to the severity of acute neurological deficits (NIHSS score), infarct volume, brain edema, hemorrhagic transformation, occurrence of progressive stroke, and clinical prognosis at 3 months (mRS score), to evaluate the predictive value of these molecules for clinical outcomes after AIS.

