5.3 Determining sample size

Assuming a 40% probability of poor prognosis at 3 months after AIS, with an OR of 2.0 for high KLK10 expression and a correlation coefficient of 0.5 between KLK10 and other influencing factors, a significance level of 0.05, and a test power of 0.8, the required sample size is calculated using PASS11 software's Logistic Regression module. A total of 182 AIS cases are needed. Additionally, 91 age- and gender-matched individuals will be selected as healthy controls in a 2:1 ratio.

6. Research subjects

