6.1 Inclusion Criteria

Inclusion criteria for AIS patients:

- Selection of 182 patients with first-ever acute ischemic stroke (AIS) who are hospitalized at our hospital, aged ≥ 18 years, with no restriction on gender;
- Patients must be admitted within 24 hours of the onset of AIS;
- Diagnosis must be confirmed by cranial magnetic resonance imaging (MRI) or computed tomography (CT);
- All enrolled patients must provide written informed consent.

Inclusion criteria for healthy controls:

- Age and gender matched;
- No organic diseases;
- Written informed consent must be signed

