10.5 Baseline Descriptive Analysis

Descriptive statistics are used to compare demographic characteristics and laboratory indicators at baseline between groups. Continuous variables such as age, blood pressure, blood glucose levels, infarct volume, ASPECTS score, neurological function (NIHSS) score, and levels of neuroinflammatory molecules (KLK10, sTREM2, and GFAP) are expressed as mean (standard deviation) or median (interquartile range). Categorical variables such as the presence of hypertension, diabetes, hyperlipidemia, history of stroke, and occurrence of malignant brain edema are expressed as n (percentage). Fisher's exact test is used to assess differences in categorical variables, and the Kruskal-Wallis Rank Sum test is used to detect differences in continuous variables..

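### Controls are matched on age and sex, but no planned patient-control test uses either factor, and sections 10.1 and 10.5 name different tests; the descriptive marker comparison is conservative and loses some power

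*Combined protocol and SAP*

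**What the plan says.** Section 5.3 sets the control group: "91 age- and gender-matched individuals will be selected as healthy controls in a 2:1 ratio". Section 6.1 adds only "Age and gender matched". Neither says whether matching is individual or by frequency, and no age tolerance is given.

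Section 5.1 states the use of the marker data: "The dynamic changes and differential expression characteristics of a group of neuroinflammatory molecules, including KLK10, sTREM2, and GFAP in plasma will be observed".

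Two sections give tests for comparing groups:

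- Section 10.1: "For comparing two groups of measurement data with normal distribution and equal variance, an independent two-sample t-test is used", and "for comparing two groups of measurement data not conforming to normal distribution and equal variance, a non-parametric Mann-Whitney U test is used". The level is set for every test: "All tests are two-tailed, with $P < 0.05$ considered statistically significant".
- Section 10.5, which lists KLK10, sTREM2 and GFAP among the variables to be compared: "the Kruskal-Wallis Rank Sum test is used to detect differences in continuous variables".

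No paired, stratified, conditional or age- and sex-adjusted comparison of patients with controls appears anywhere. The logistic models in sections 10.2 and 10.3 concern outcomes that only patients can have.

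**The concern.** Matching makes the two groups alike in age and sex, so those factors contribute little to the difference in mean marker level. An independent-samples test still counts the variance due to age and sex in its standard error. The standard error is then larger than the true sampling variation of the difference. The test rejects too rarely under the null and has less power than the design could give. The 91 controls have no other analytic use in the plan, so the benefit of matching them is partly thrown away.

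The two sections also leave the analyst a choice. With two groups, Kruskal-Wallis is in essence the Mann-Whitney test, so for continuous data the conflict arises when the data are judged normal with equal variance: section 10.1 then gives a t-test and section 10.5 a rank test.

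A smaller gap concerns roughly normal data with unequal variance. Read as the complement of the t-test condition, section 10.1 sends that case to Mann-Whitney. Read as covering non-normal data only, it gives that case no test.

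**Working it through.** The plan has no power or precision figure for the patient-control comparison, so there is nothing to reproduce. The control number is simply 182 / 2 = 91.

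**Inputs from the documents:** 182 patients and 91 controls (section 5.3); two-sided 5% level (section 10.1).

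**Assumptions, not in the documents:** age and sex explain a share R² = 0.1, 0.2 or 0.3 of log-marker variance; the true difference is 0.35 SD; matching is close enough to remove age and sex from the difference in means.

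**Step 1, standard error in SD units.** The unadjusted test uses √(1/182 + 1/91) = 0.1284. The true value under matching is 0.1284 × √(1 − R²).

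**Step 2, actual type I error** of the unadjusted test: 2 × [1 − Φ(1.96 / √(1 − R²))].

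**Step 3, power.** Unadjusted: Φ[(0.35 − 1.96 × 0.1284) / true SE], with numerator 0.0984. Adjusted: Φ[0.35 / true SE − 1.96].

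| R² | True SE | Unadjusted SE too large by | Type I error | Power, unadjusted | Power, adjusted | Gap (points) |
|---|---|---|---|---|---|---|
| 0.1 | 0.1218 | 5% | 3.9% | Φ(0.81) = 79% | Φ(0.91) = 82% | 3 |
| 0.2 | 0.1148 | 12% | 2.8% | Φ(0.86) = 80% | Φ(1.09) = 86% | 6 |
| 0.3 | 0.1074 | 20% | 1.9% | Φ(0.92) = 82% | Φ(1.30) = 90% | 8 |

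At R² = 0 the two standard errors are equal and nothing is lost.

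**Step 4, simulation check.** 91 sets of two patients and one control were simulated (20,000 runs; 8,000 for Mann-Whitney).

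- At within-set correlations of 0, 0.1, 0.2 and 0.3 the independent t-test rejected a true null in 5.0%, 4.0%, 2.8% and 2.1% of runs. Mann-Whitney was almost the same.
- A matched-set t-test stayed between 4.9% and 5.4%.
- At a 0.36 SD difference, power was 81% unpaired against 83% matched at correlation 0.1, and 84% against 91% at 0.3.

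**Step 5, secondary point.** For normal data with equal means, 182 v 91 (10,000 runs), the rejection rates at the nominal 5% level were:

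| Patient SD / control SD | Mann-Whitney |
|---|---|
| 0.5 | 8.6% |
| 0.67 | 7.2% |
| 1.5 | 3.8% |
| 2 | 3.2% |

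Welch's t-test stayed between 4.7% and 5.2% over all ratios tried (0.25 to 4). The SD ratios are assumptions.

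**The case against.** The strongest reply is that nothing important rests on this comparison. Section 10.1 speaks of two groups without naming patients and controls. Section 10.5 does not name its groups either, and several of its variables (infarct volume, ASPECTS, NIHSS) exist only for patients. No listed objective is a patient-control contrast, and the endpoints in sections 9.1 and 9.2 are associations among patients, analysed by logistic regression and ROC curves. All of this stands and limits the point to a descriptive comparison. It does not remove it: a matched control group is recruited and measured, and no other test in the plan could be applied to it.

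The matching may also be by frequency and loose. The loss would then be smaller than tabulated. Age and sex would still belong in the analysis.

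A reader might infer three stronger points that the documents do not support:

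- **That ignoring the matching produces false positives.** It does the reverse: the error is on the conservative side only.
- **That planned confidence intervals are too wide.** Section 10.1 plans no interval for a group difference; intervals are planned only for odds ratios.
- **That Mann-Whitney makes the good- v poor-outcome comparisons anti-conservative.** Splitting 182 at the assumed 40% into 73 and 109 gives 7.6% and 8.9% in simulation if the smaller group has two or three times the SD. But section 7.4 puts mRS 3 in neither outcome group, so 109 is not supported. The SD ratios are assumed, and section 10.2 tests outcome associations by logistic regression.

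Mann-Whitney also remains valid for the null of identical distributions; its departure from 5% concerns equal means. If the markers are skewed, they reach it through non-normality anyway. This is why the Welch change is secondary.

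**Conclusion.** The point holds as a modest loss of efficiency and an unresolved choice of test in the descriptive patient-control comparison. Its size depends entirely on how strongly each marker varies with age and sex, which the documents do not say. The tabulated range assumes R² of 0.1 to 0.3, close matching and a 0.35 SD difference. The application to patients v controls is inferred from the absence of any other suitable test, since no section states it.

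No primary or secondary conclusion is at risk. The change is worth making because it costs almost nothing and settles the conflict between the two sections. The gap for normal data with unequal variance is real on either reading of section 10.1, but its direction depends on which group is more variable and its practical effect is unknown.

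**What to change.** 1. State in section 6.1 whether matching is individual or by frequency, and the age tolerance.
2. For each marker, compare patients with controls by linear regression of the log-transformed level on group, with age (continuous) and sex as covariates. Add a matched-set term if matching is individual. Name the patient sampling time used, since section 5.1 has three patient samples and one control sample.
3. Report the adjusted geometric-mean ratio with a 95% confidence interval and robust (HC3) standard errors.
4. Make sections 10.1 and 10.5 name this one method for the patient-control comparison, and remove the conflicting rules.
5. Secondary: for other two-group comparisons of roughly normal data, use Welch's t-test, which covers unequal variance.

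The cost is plan wording only, settled before the marker data are analysed. Age and sex must already be recorded to do the matching, so no new data or participants are needed.

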10.2 Primary Endpoint Analysis

Investigate the association between plasma KLK10, sTREM2, and GFAP levels and functional prognosis at 3 months: Univariate and multivariate logistic regression models are used to evaluate independent predictors, and odds ratios (OR) with 95% confidence intervals (CI) are calculated. ROC curves are plotted and the area under the curve (AUC) is calculated.

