7.1.4 Items and frequency of clinical and laboratory examinations to be conducted

- 1) Collect reports of complete blood count and biochemical tests upon admission: including neutrophil and lymphocyte counts, blood glucose, creatinine, and high-sensitivity C-reactive protein levels.
- 2) Collect blood pressure information upon admission.
- 3) Collect reports of cranial MRI or CT scans upon admission, and record the Alberta Stroke Program Early CT Score (ASPECTS) (0-10 points).
- 4) Measure levels of neuroinflammatory markers KLK10, sTREM2, and GFAP in plasma at admission, and at 24 hours and 7 days after stroke
- 5) Assess the degree of neurological impairment using the National Institutes of Health Stroke Scale (NIHSS) at admission, and at 24 hours, 4 days, 7 days, and discharge after stroke.
- 6) Collect information on infarct volume within 7 days after stroke, measured using diffusion-weighted imaging (DWI) (J Neuroinflammation. 2020 Apr 7;17(1):107).
- 7) Collect information on brain edema grading within 7 days after stroke, measured using non-contrast cranial CT scans. The severity of brain edema in AIS patients is assessed with a score of 0-3 based on our established method (Clin Neurol Neurosurg. 2022 Nov 2;223:107507).
- 8) Collect information on hemorrhagic transformation within 7 days after stroke, measured using non-contrast cranial CT scans.
- 9) Record the Modified Rankin Scale (mRS) score at 3 months after stroke.

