7.4 Follow-up and Compliance

3 months mRS Score: 0-2 indicates a good outcome, 4-6 indicates a poor outcome
Grading Description:

- 0: No symptoms at all

- 1: No significant disability despite symptoms; able to carry out all usual duties and activities
- 2: Slight disability; unable to carry out all previous activities but able to look after own affairs without assistance
- 3: Moderate disability; requiring some help but able to walk without assistance
- 4: Severe disability; unable to walk without assistance and unable to attend to own bodily needs without assistance
- 5: Very severe disability; bedridden, incontinent, and requiring constant nursing care and attention
- 6: Death

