9.1 Primary Endpoint Evaluation

The study examines the association between plasma levels of KLK10, sTREM2, and GFAP with favorable functional outcomes at 3 months after stroke onset.

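### The 3-month mRS is recorded on its full 0-6 scale, but no planned analysis uses the ordering; a supporting proportional-odds model would recover that information at little cost.

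*Combined protocol and SAP*

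**What the plan says.** All references are to the combined protocol and SAP.

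- **Collection.** Section 7.1.4 says to "Record the Modified Rankin Scale (mRS) score at 3 months after stroke", and section 7.4 lists all seven grades, from no symptoms (0) to death (6).
- **Split.** Section 7.4 also states: "3 months mRS Score: 0-2 indicates a good outcome, 4-6 indicates a poor outcome". Grade 3 is described but placed in neither class.
- **Endpoint.** Section 9.1 makes the primary endpoint the "association between plasma levels of KLK10, sTREM2, and GFAP with favorable functional outcomes at 3 months after stroke onset".
- **Sample size.** Section 5.3 begins "Assuming a 40% probability of poor prognosis at 3 months after AIS" and takes an OR of 2.0 for high KLK10, a correlation of 0.5 with other factors, alpha 0.05 and power 0.8, arriving at 182 patients.
- **Analysis.** Section 10.2: "Investigate the association between plasma KLK10, sTREM2, and GFAP levels and functional prognosis at 3 months: Univariate and multivariate logistic regression models are used", with ORs and 95% CIs as the output. It then adds "ROC curves are plotted and the area under the curve (AUC) is calculated".
- **Second use of the scale.** Sections 9.2 and 10.3 analyse 3-month mortality, again by logistic regression with ROC curves.

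Nothing in Section 10 mentions an ordinal, shift or proportional-odds analysis, and no reason for splitting the scale is given.

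**The concern.** Section 10.2 names logistic regression without saying whether the outcome is binary or ordinal. Read with 5.3, 7.4 and 9.1, the natural meaning is a binary outcome. Within the primary analysis, a patient with no symptoms then counts the same as one with slight disability, and grade 4 counts the same as death. A marker that moves patients along the scale without carrying them over the cut contributes nothing.

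At stake is the precision of the marker-outcome association, which is the study's main question. The data needed for a more precise estimate are already being collected.

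**Working it through.** **1. The plan's own sample size.** Inputs from 5.3: poor-outcome rate 0.40, OR 2.0, R = 0.5 (R-squared 0.25), power 0.8; two-sided alpha 0.05 from 5.3 and 10.1. For a continuous marker with OR per SD:

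n = (1.96 + 0.842)² / [0.40 × 0.60 × (ln 2)²] / (1 − 0.25) = 7.849 / (0.24 × 0.4805) / 0.75 = 68.07 / 0.75 = 90.8, i.e. 91.

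The stated 182 is not reproduced. It equals twice this result (181.5, rounded up). For a two-level marker with an assumed 50% high, the usual approximations give about 353 to 405. This is a separate matter, but it shows that 5.3 does not settle how KLK10 enters the model, and step 3 depends on that.

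**2. Information in the split and in the full scale.** Near the null, information per patient for a marker with unit SD is:

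- binary: p(1 − p) = 0.40 × 0.60 = 0.24
- proportional odds: (1 − Σ p_k³) / 3, where p_k are the shares in the seven grades

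The documents give no shares, so those below are assumptions. Each has 40% in grades 3 to 6, that is, grade 3 counted as poor.

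| Assumed shares, grades 0 to 6 (%) | Σ p_k³ | Ordinal information | Ratio to 0.24 | 182 act like |
|---|---|---|---|---|
| 20/20/20/10/10/10/10 | 0.0280 | 0.324 | 1.35 | 246 |
| 12/24/24/14/12/5/9 | 0.0347 | 0.322 | 1.34 | 244 |
| 5/45/10/10/15/5/10 | 0.0978 | 0.301 | 1.25 | 228 |
| 5/50/5/5/25/5/5 | 0.1413 | 0.286 | 1.19 | 217 |

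The first row is the ceiling for a 60/40 split of this scale. Over 200,000 random 60/40 distributions the median ratio was 1.32, with 5th to 95th percentiles of 1.25 to 1.34; the lowest was 1.09. A range of 1.2 to 1.35 is therefore reasonable, but its lower end is not a strict floor.

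**3. Power at 182 patients.** Power = Φ(ln OR × √[182 × 0.24 × ratio × v × (1 − 0.25)] − 1.96), where v is the marker variance: 1 for a per-SD effect, 0.25 for a marker with 50% high. The ratio is 1 for the split.

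| Marker and effect | Split | Ordinal, ratio 1.19 | Ordinal, ratio 1.34 |
|---|---|---|---|
| OR 2.0 per SD | 98% | 99% | over 99% |
| OR 2.0, high v. low (50% high assumed) | 51% | 58% | 63% |
| OR 1.5 per SD (assumed) | 64% | 72% | 77% |

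For example, the split at OR 1.5 gives 0.4055 × √32.76 = 2.32, and Φ(2.32 − 1.96) = 64%. At OR 2.0 per SD the ratio itself is larger, about 1.36 to 1.57, but with power already near 98% this makes no practical difference.

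**4. Grade 3.** The figures above count grade 3 as poor, which 7.4 does not do. If grade 3 were dropped and 5% to 15% of patients scored 3 (assumed), 182 × 0.95 = 173 down to 182 × 0.85 = 155 patients would be analysed. At OR 2.0 per SD the ordinal model would then carry about 1.35 to 1.61 times the information of the reduced split.

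**The case against.** The stated aim is prediction of a favourable outcome, and a conventional ROC curve needs two classes. The split fits that aim and is easy to interpret clinically. This stands: dichotomising is a choice with a cost, not a mistake, and the binary analysis should remain primary.

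It also stands that an added ordinal model leaves the power of the binary test where it was, and that it adds at least one test for each of three markers, more if admission and 24-hour levels are both analysed. The plan states no multiplicity control.

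A reader might infer that everything the study learns from the mRS rests on one boundary, and that death is never told apart from severe disability. The documents do not support this, because 9.2 and 10.3 analyse 3-month mortality separately, which is a second cut of the same scale. What remains true is that both uses are binary and neither uses the ordering.

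A reader might also take the gain to be a firm third. That is close to the ceiling of 1.35 and rests on grade shares that the documents do not give.

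**Conclusion.** The point holds as a modest, inexpensive improvement. The full scale is collected, the plan implies two binary cuts of it, and no analysis uses the order of the grades. Under proportional odds with 40% poor and grade 3 counted as poor, the ordinal model carries about 1.2 to 1.35 times the information near the null.

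Whether that matters depends on the unstated form of KLK10. If the 2.0 in 5.3 is per SD, power is already about 98% and the gain is trivial. If it compares high with low, or the true effect is smaller, the gain is about 7 to 13 percentage points (51% to 58-63%; 64% to 72-77%). It would be wrong to infer that the primary analysis is invalid or that the study is underpowered because of the split: the first confuses efficiency with validity, and the second depends on a marker coding that the plan does not give.

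The unclassified grade 3 in 7.4 is a separate defect. It must be reconciled with the 40% in 5.3 and the endpoint in 9.1 whichever model is used.

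**What to change.** - State in 10.2 that the primary model is binary logistic regression with ROC/AUC, and keep it as primary.
- Add to 10.2 one pre-specified supporting analysis: proportional-odds regression of mRS 0-6 on each marker, with the same covariates, reported as a common OR with 95% CI. Show the cut-specific ORs beside it as a check of proportionality.
- State how each marker enters the models (continuous per SD, or high/low with a fixed threshold).
- Reconcile the class of grade 3 in 7.4. The ordinal model uses those patients in any case.

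**Cost.** SAP wording and one extra model per marker, with no new visits, patients or assays. The downsides are that the common OR assumes a similar effect at every cut, and that each marker gains at least one more test. Label the model as supporting, so that it is read for precision of the association and not as a second chance at significance.

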1.1 Abstract

Study Name: Predictive Role of Early Blood KLK10 and Other Neuroinflammatory Molecules on Clinical Outcomes of Acute Ischemic Stroke

Research Introduction: This study aims to investigate the dynamic changes and differential expression characteristics of neuroinflammatory molecules such as kallikrein-related peptidase 10 (KLK10), soluble triggering receptor expressed on myeloid cells 2 (sTREM2), and glial fibrillary acidic protein (GFAP) in the plasma of patients with first-ever anterior circulation acute ischemic stroke (AIS). It will analyze the correlation between these molecules and the severity of neurological deficits, infarct volume, brain edema, hemorrhagic transformation, progressive stroke, and clinical outcomes at three months. The goal is to assess the predictive value of these molecules for AIS prognosis, providing guidance for early treatment and new molecular targets for prevention and treatment.

Study Objectives :
1. To study the correlation between early plasma changes in neuroinflammatory molecules like KLK10 and clinical outcomes at three months post-AIS.
2. To investigate the relationship between early plasma changes in these molecules and hemorrhagic transformation post-AIS.
3. To explore the correlation between early plasma changes in these molecules and the occurrence of progressive stroke post-AIS.

Study subjects: 182 patients with first-ever anterior circulation AIS, regardless of gender and age, along with 91 age- and gender-matched healthy individuals as controls.

[figure not shown]
Research Site: Ruijin Hospital North Campus

Study Interventions : Non-interventional studies

Study duration: April 2024 - March 2025

Participant Duration: 3 months

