Astrocytes, which also play a role in regulating brain inflammation, are the main glial cells in the central nervous system and are widely distributed throughout the brain. In their resting state, astrocytes provide structural and functional support to neurons, regulate synaptic activity by releasing gliotransmitters, and participate in synapse formation and remodeling (*Neurochem Int.* 2023;162:105456. *Neuroscience*, 2019, 396:73-78). After cerebral ischemia, astrocytes become activated and proliferate, limiting immune cell infiltration, repairing damaged BBB, and restoring stability in the brain's internal environment (*Front Immunol.* 2020, 11:1024. *Neurosci Lett*, 2019; 689: 45-55). Our studies and others have shown that astrocytes are extensively lost in the infarct core after cerebral ischemia, peaking at 48-98 hours post-stroke. The GFAP expressed by astrocytes can be released into peripheral blood, and its levels in the blood can reflect cell necrosis and BBB disruption (*Transl Stroke Res.* 2010;1(4):246-51) and can serve as molecular markers for distinguishing ischemic and hemorrhagic strokes (*Diagnostics (Basel).* 2023 Aug 25;13(17):2757).

The pathological damage mechanism of stroke is highly complex. Single neuroinflammatory molecules in plasma, whether sTREM2 or GFAP, are insufficient for predicting AIS prognosis. However, measuring a set of neuroinflammatory molecule levels may more accurately reflect the degree of neuropathological damage in AIS. Therefore, we propose that "early changes in plasma levels of KLK10, sTREM2, and GFAP, among other neuroinflammatory molecules, can effectively predict the clinical prognosis of AIS."

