3.2 Main Participants

Serial number	Name	gender	age	job title	Specialty	Whether GCP Training	Roles in the research (eg. PI, sub-I, CRC)
1	[name]	male	51	Chief Physician	Neurology	yes	PI
2	[name]	male	38	Deputy Chief Physician	Neurology	yes	sub-I
3	[name]	male	38	Indications Physician	Neurology	yes	sub-I
4	[name]	male	33	Indications Physician	Neurology	yes	CRC
5	[name]	female	29	Hospitalization Physician	Neurology	yes	CRC

4. Research Objectives

- 1) To determine whether early KLK10 and a group of neuroinflammatory molecules in plasma can serve as molecular markers for predicting clinical prognosis in AIS (Acute Ischemic Stroke).
- 2) To determine whether early KLK10 and a group of neuroinflammatory molecules in blood can serve as molecular markers for predicting hemorrhagic transformation in AIS.

5. Study Design

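### The plan sets out to evaluate prediction by a group of markers but reports only an uncorrected AUC with no stated score, which would usually favour the three-marker set over KLK10 even if sTREM2 and GFAP add nothing

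*Combined protocol and SAP*

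**What the plan says.** The abstract (1.1) states the aim: "The goal is to assess the predictive value of these molecules for AIS prognosis". Section 2.2 gives the reason for a panel: "Single neuroinflammatory molecules in plasma, whether sTREM2 or GFAP, are insufficient for predicting AIS prognosis", whereas "measuring a set of neuroinflammatory molecule levels may more accurately reflect the degree of neuropathological damage in AIS". The first objective in Section 4 is "To determine whether early KLK10 and a group of neuroinflammatory molecules in plasma can serve as molecular markers for predicting clinical prognosis in AIS", and Section 5.1 sets out "to evaluate the predictive value of these molecules for clinical outcomes after AIS".

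The primary analysis (10.2) is univariate and multivariate logistic regression with odds ratios and 95% CIs, after which "ROC curves are plotted and the area under the curve (AUC) is calculated". Section 10.3 repeats this for death, hemorrhagic transformation and progressive stroke.

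No section says whether an AUC belongs to a raw marker, a three-marker model or a larger model. None plans a comparison of AUCs or of nested models, a bootstrap, cross-validation or an outside validation sample. Adjustment is implied by the search for independent predictors and by the sample-size assumption of "a correlation coefficient of 0.5 between KLK10 and other influencing factors" (5.3), but no covariate is named. Section 10.5 lists age, NIHSS, ASPECTS and other baseline variables for description and group comparison only.

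**The concern.** A reader of the results will judge the panel by its AUC, probably set beside the AUC of KLK10. To draw one ROC curve for three markers, they must be combined into one score, and the usual score is the linear predictor of a logistic model fitted to the same patients. Such a model adapts to chance patterns in those patients. Its AUC is then too high, and adding markers nearly always raises it, whether or not they carry information.

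The risk is therefore that the paper reports a panel advantage that would not appear in new patients. The size is modest for the primary outcome with few terms. It is larger for death and hemorrhagic transformation if those events are rarer, and larger still if many covariates enter the model.

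**Working it through.** **1. The plan's own figure.** Section 5.3 gives P = 0.40, OR = 2.0, two-sided alpha 0.05, power 0.80, correlation 0.5 and n = 182. For a continuous covariate, n = (z_alpha + z_power)² / [P(1-P)(ln OR)²] / (1-R²).
- Numerator: (1.960 + 0.842)² = 7.849. Denominator: 0.24 × 0.6931² = 0.1153. Ratio: 68.1.
- R² = 0.25 gives 68.1/0.75 = 91; R² = 0.50 gives 68.1/0.50 = 136 (137 rounded up).
- 182 appears with power 0.90 and R² = 0.50: 91.12/0.50 = 182.25.

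So 182 is not reproduced at the stated power of 0.80. The present point does not depend on this. It uses 182 patients and 0.40 × 182 = 73 events.

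**2. Assumptions added for the simulations.** ORs are per SD (5.3 gives no unit). Age has OR 1.5 and NIHSS OR 2. The correlation among NIHSS and the markers is 0, 0.3 or 0.5. None of these comes from the documents.

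**3. Extra markers add nothing.** KLK10 has OR 2.0 or 1.3; sTREM2 and GFAP have OR 1.0. The set (age, NIHSS, three markers) is compared with age, NIHSS and KLK10, at N = 182 and 40% events, with 600 datasets per setting, repeated with separate code.
- In-sample AUC of the set higher than that with KLK10: about 84-90% of studies.
- Mean apparent gain: +0.005 to +0.008.
- Mean gain in 20,000 new patients: about -0.006 (range -0.008 to -0.005).

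**4. Optimism = apparent AUC minus AUC in new patients.**
- One predictor, 40% events: 0.679 - 0.680 = -0.001, so essentially none.
- Three predictors, one of them real with OR 2.0: 0.690 - 0.669 = 0.021.
- Five terms (age, NIHSS, three markers), 40% events: about 0.02-0.03.
- Five terms, assumed 10% event rate (about 18 events): about 0.04-0.07.

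**5. What the planned multivariable tests can do.** Suppose all three markers enter one model with age and NIHSS.
- If sTREM2 and GFAP add nothing, at least one has Wald P < 0.05 in 8-12% of studies, close to the 1 - 0.95² = 9.75% expected for two tests.
- If each has OR 1.3, at least one is significant in 41-56%, against 38-49% for the likelihood-ratio test of the set versus base + KLK10 in the same runs.
- If NIHSS is left out and is correlated with the markers, the false-positive rate rises to 18-23%.

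**6. Does the remedy work?** Bootstrap-corrected AUCs came within 0.005 of the new-patient AUC in all six settings tried; for example, 0.774 apparent, 0.750 corrected, 0.748 in new patients. Power at N = 182 and 40% events, for correlation 0 / 0.3 / 0.5:

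| Marker ORs (KLK10, sTREM2, GFAP) | Set vs base + KLK10 | Set vs all three single-marker models |
|---|---|---|
| 2.0, 1.3, 1.3 | 0.504 / 0.464 / 0.372 | 0.494 / 0.428 / 0.297 |
| 1.3, 1.3, 1.3 | 0.511 / 0.511 / 0.412 | 0.235 / 0.173 / 0.084 |
| 2.0, 1.0, 1.0 (false claim) | not needed here | 0.050 / 0.053 / 0.046 |

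The last row shows that requiring all three comparisons at P < 0.05 keeps the false-claim rate near 5% without further adjustment. The corrected AUC difference versus base + KLK10 has SD 0.012-0.025, so its 95% CI is about ±1.96 × SD = ±0.02 to 0.05, against a true gain near 0.01.

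**The case against.** The strongest reply has four parts.

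- **The panel's superiority is rationale, not an endpoint.** Only Section 2.2 contrasts single markers with a set. Its comparative wording concerns reflecting damage, and it names sTREM2 and GFAP as the insufficient single markers. The objectives ask whether the molecules predict. This stands: a reader might infer that the plan promises a test of set against single marker and omits it, but no listed endpoint says so. What remains is that the plan undertakes to evaluate prediction by a group and offers the AUC as its only measure of discrimination.
- **The planned regression already tests added value.** This also stands. A reader might infer that the plan has no means of showing whether the set improves on KLK10. Step 5 shows otherwise, provided the three markers share one model with a clinical covariate such as NIHSS. The plan does not state that condition, and the tests do not repair the AUC.
- **A raw single-marker AUC is not biased.** True if its direction is fixed in advance. The complaint about optimism applies only to fitted scores.
- **The bias is small and the remedy has low power.** Both are true for the primary outcome with few terms. But the spurious gain is about as large as the gain one could hope to detect, so a small bias still decides which model looks better.

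**Conclusion.** The point holds in this limited form: the AUC as planned is uncorrected and not tied to a stated score, and it cannot support a comparison between the set and a single marker. With no true gain, the set would still look better than KLK10 in about 84-90% of studies, by +0.005 to +0.008. Absolute optimism is about 0.02-0.03 for five terms at 40% events and about 0.04-0.07 if only 10% have the event.

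The number of patients and the 40% rate come from Section 5.3. ORs per SD, the effects of age and NIHSS, the correlations and the 10% rate are assumed. Sizes change with these assumptions; the direction does not.

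The documents do not support reading the whole plan as unable to detect added value, nor every AUC as inflated. Section 5.1 counts two draws as early ("The early changes (at admission and 24 hours after onset) of these neuroinflammatory molecules in plasma will be compared and analyzed") without choosing one for the primary model, and three markers share the primary endpoint without a multiplicity rule. These are side points that do not carry the finding. It is a change that should be made, not a flaw that invalidates the study.

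**What to change.** In Section 10.2:

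1. Prespecify one model with baseline covariates already collected (for example age and admission NIHSS) plus KLK10, sTREM2 and GFAP.
2. Compare it by likelihood-ratio test with the base model and with base + each single marker. Claim that the set beats single markers only if all three single-marker comparisons reach P < 0.05.
3. State which score each AUC uses. For raw markers, fix the direction in advance.
4. Report model-based AUCs, and the AUC differences of the set versus base and versus base + each single marker, with bootstrap optimism correction and 95% CI.

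Use the same correction for model-based AUCs in Section 10.3.

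The cost is SAP wording and a little more analysis, with no new data. Reported AUCs fall by about 0.02-0.03 for a five-term model at 40% events. Power is limited: about 37-51% against base + KLK10 if sTREM2 and GFAP each have OR 1.3 per SD, and less if fewer patients are analysable (Section 7.4 puts mRS 3 in neither outcome class). A null result must therefore be reported with its CI and not read as proof of no added value.
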